9.4.3 Electrocardiogram

A summary of raw values and change from baseline values will be provided by treatment at each scheduled visit during the TE period for the following standard 12-lead ECG measurements: PR, QT, QRS, QTcF [QTcF = QT/RR^{0.33}], and HR. In addition, the number and percentage of subjects by maximum on-treatment value of QT/QTcF intervals, categorized as \leq 450 msec, $>$ 450 msec and \leq 480 msec, $>$ 480 msec and \leq 500 msec, and $>$ 500 msec, as well as maximum on-treatment change from baseline value of QT/QTcF intervals, categorized as \leq 0 msec, $>$ 0 and \leq 30 msec, $>$ 30 and \leq 60 msec, and $>$ 60 msec, will be provided.

The threshold value criteria for ECG data are provided in [Appendix D](#). A listing containing individual subject measurements meeting the threshold value criteria at any visit will be provided. For each subject in the listing, ECG measurements at all visits will be included.

Clinically significant ECG abnormalities occurring during the study through the Safety Follow-up Visit will be recorded as AEs.

9.4.4 Vital Signs

The raw values and change from baseline values during the TE period will be summarized by treatment at each scheduled visit: systolic and diastolic blood pressure (mm Hg), body temperature (°C), pulse rate (beats per minute), and respiratory rate (breaths per minute).

The threshold value criteria for vital signs data are provided in [Appendix D](#). A listing containing individual subject measurements meeting the threshold value criteria at any visit will be provided. For each subject in the listing, vital signs at all visits will be included.

Clinically significant abnormal findings in vital signs will be reported as AEs.

9.4.5 C-SSRS

The responses to the first two questions in the C-SSRS will be summarized by treatment at baseline and at each scheduled visit:

- Wish to be dead
- Non-specific active suicidal thoughts

Subjects with “yes” response to either of the first two questions at baseline and at any scheduled visit will be listed separately. For each subject in the listing, responses to all questions in the C-SSRS at all visits will be included.

9.4.6 Physical Examination

PE results will be presented in individual subject data listings only. Clinically relevant results identified after screening will be reported as AEs.

9.4.7 Neurological Examination

Neurological Examination results will be presented in a data listing only.

9.4.8 Bedside Sensory Testing Kit

Bedside Sensory Testing Kit results will be presented in a data listing only.

10 SUMMARY OF INTERIM AND IDMC ANALYSES

Not applicable.

12 LIST OF APPENDICES

Appendix A: Analysis Visit Windows for Safety and Efficacy Assessments

Table 12-1 Analysis Visit Windows for Safety and Efficacy Assessments

Assessment	Visit ¹	Target Study Day per the protocol	Analysis Visit Window (in study days)
Safety Assessment			
Hematology	Baseline	1	[Screening visit, Pre-dose Day 1]
Serum Chemistry	Week 3	22	[1*, 32]
	Week 6	43	[33, 57]
	Safety Follow-up Visit	N/A	Nominal
Coagulation	Baseline	N/A	[Screening visit, Pre-dose Day 1]
	Week 6	43	[1*, 57]
	Safety Follow-up Visit	N/A	Nominal
Standard 12-Lead ECG	Baseline	1	[Screening visit, Pre-dose Day 1]
	Day 7	7	[1*, 57]
	Safety Follow-up Visit	N/A	Nominal
Vital Sign	Baseline	1	1
	Day 7	7	[2, 14]
	Week 3	22	[15, 32]
	Week 6	43	[33, 57]
	Safety Follow-up Visit	N/A	Nominal
C-SSRS	Baseline	1	[-1, 1]
	Day 7	7	[2, 14]
	Week 3	22	[15, 32]
	Week 6	43	[33, 57]
	Safety Follow-up Visit	N/A	Nominal

Table 12-1 Analysis Visit Windows for Safety and Efficacy Assessments

Assessment	Visit ¹	Target Study Day per the protocol	Analysis Visit Window (in study days)
Efficacy Assessment			
NRS via daily diary	Baseline	N/A	[-7, -1] ²
DSIS via daily diary	Week 1	N/A	[1*, 7]
	Week 2	N/A	[8, 14]
	Week 3	N/A	[15, 21]
	Week 4	N/A	[22, 28]
	Week 5	N/A	[29, 35]
	Week 6	N/A	[36, 42]
NRS reported at study visits	Baseline	1	Before first dose of study drug
PGIC			
	Day 7	7	[1*, 14]
	Week 3	22	[15, 32]
	Week 6	43	[33, 57]
	Safety Follow-up Visit	N/A	Follow the individual visit window to be mapped to individual visits if measured before / on Day 57 or remain as SFU if otherwise.

1* only include day 1 post-dose measurements.

¹ Visit name for analysis purpose is used to report data in tables and figures.

²Only include 7 day measurements before the randomization day.

Notes:

The analysis visit windows will be applied using the following rules for both scheduled and unscheduled visits:

1. If no numerical measurement is available within a visit window, the measurement will be considered missing for the visit.
2. If there is more than 1 numerical measurement available within the same visit window, use the following rules:
 - a. a. For efficacy assessments: if there are multiple measurements within a visit window,
 - i. The measurement closest to the target day will be used; or
 - ii. If there are multiple measurements within the same distance from the target day, the latest measurement will be used.
 - b. For safety assessments: if there are multiple measurements within a visit window,
 - i. The measurement closest to the target day will be used; or
 - ii. If there are multiple measurements within the same distance from the target day, the latest measurement will be used.
3. When define efficacy and safety at baseline, refer to the generic baseline definition in Section 9.1. If the first dose time is missing, baseline will be defined as the most recent nonmissing measurement collected before the date of the first dose of study drug. For vital sign, there is no time collected and Day 1 will be baseline. For CSSR-S, baseline will be defined as the most recent nonmissing measurement collected before/on Day 1.
4. If the first dose time is missing, use the first dose date to determine post-dose measurements.

Appendix B: Imputation Rules for Missing Prior/Concomitant Medication Dates

Imputation rules for missing or partial medication start/stop dates are defined below:

1. Missing or partial medication start date:
 - a. If only DAY is missing, use the first day of the month.
 - b. If DAY and Month are both missing, use the first day of the year.
 - c. If DAY, Month and Year are all missing, use a date before the first dose date.
2. Missing or partial medication stop date:
 - a. If only DAY is missing, use the last day of the month.
 - b. If DAY and Month are both missing, use the last day of the year.
 - c. If DAY, Month and year are all missing, assign ‘continuing’ status to stop date.

In summary, the prior and/or concomitant categorization of a medication is described below.

Table 12-2 Prior and/or Concomitant Categorization of a Medication

Medication Start Date	Medication Stop Date		
	< First Dose Date of Study Drug	≥ First Dose Date and ≤ End Date of TE Period	
< First dose date of study drug	P		PC
≥ First dose date and	-		C
≤ End date of TE period			

C: Concomitant; P: Prior

Appendix C: Imputation Rules for Missing AE dates

Imputation rules for missing or partial AE start date are defined below:

If only Day of AE start date is missing:

If the AE start year and month are the same as that for the first dose date, then:

- If the full (or partial) AE end date is NOT before the first dose date or AE end date is missing, then impute the AE start day as the day of first dose date; otherwise, impute the AE start day as 1.
- Otherwise, impute the AE start day as 1.

Compare the imputed AE start date with TE period to determine whether the AE is pretreatment AE, or TEAE.

If Day and Month of AE start date are missing:

If AE start year is the same as first dose year, then:

- If the full (or partial) AE end date is NOT before the first dose date or AE end date is missing, then impute the AE start Month and Day as the Month and Day of first dose date; otherwise, impute the AE start Month as January and the Day as 1.
- Otherwise, impute the AE start MONTH as January and the DAY as 1.

Compare the imputed AE start date with TE period to determine whether the AE is pretreatment AE, or TEAE.

If Year of AE start date is missing:

If the year of AE start is missing or AE start date is completely missing then query site with no imputation. Also compare the full (or partial) AE end date to the first dose date. If the AE end date is before the first dose date then the AE should be considered as a pretreatment AE. Otherwise, the AE will be considered as TEAE.

Appendix D: Threshold Value Criteria

Table 12-3 Threshold Value Criteria for Laboratory Tests

Parameter	Comments	
Clinical Chemistry		
ALT	$\leq 3 \times \text{ULN}$ * (Not a PCS criterion) $>3x$ to $\leq 5x\text{ULN}$ $>5x$ to $\leq 8x\text{ULN}$ $>3x\text{ULN}$ $>5x\text{ULN}$ $>8x\text{ULN}$	FDA DILI Guidance Jul 2009.
AST	$\leq 3 \times \text{ULN}$ * (Not a PCS criterion) $>3x$ to $\leq 5x\text{ULN}$ $>5x$ to $\leq 8x\text{ULN}$ $>3x\text{ULN}$ $>5x\text{ULN}$ $>8x\text{ULN}$	FDA DILI Guidance Jul 2009.
ALT or AST	ALT $>3x\text{ULN}$ or AST $>3x\text{ULN}$	Vertex LFT working group 2014. To be counted within the same treatment period.
Alkaline Phosphatase	$>1.5x\text{ULN}$	FDA DILI Guidance Jul 2009.
Total Bilirubin	$>1.5x$ to $\leq 2x\text{ULN}$ $>2x\text{ULN}$	FDA DILI Guidance Jul 2009.
ALT and Total Bilirubin	ALT $>3x\text{ULN}$ and TBILI $>2x\text{ULN}$	FDA DILI Guidance Jul 2009. To be counted within a same treatment period.
AST and Total Bilirubin	AST $>3x\text{ULN}$ and TBILI $>2x\text{ULN}$	FDA DILI Guidance Jul 2009. To be counted within a same treatment period.
(ALT or AST) and Total Bilirubin	(ALT $>3x\text{ULN}$ or AST $>3x\text{ULN}$) and TBILI $>2x\text{ULN}$	Vertex LFT working group 2014. To be counted within the same treatment period.
CK	$>3x$ to $\leq 10x\text{ULN}$ $>10x\text{ULN}$	FDA criteria Feb 2005. Am J Cardiol April 2006.
Creatinine	$\geq 150 \text{ }\mu\text{mol/L}$ (Adults) $\geq 30\%$ change from baseline $\geq 100\%$ change from baseline	Benichou C., 1994.
Blood Urea Nitrogen	$\geq 17 \text{ mmol/L}$	
Chloride	$<85 \text{ mmol/L}$ $>115 \text{ mmol/L}$	
Sodium	$\leq 129 \text{ mmol/L}$ $\geq 150 \text{ mmol/L}$	

Table 12-3 Threshold Value Criteria for Laboratory Tests

Parameter		Comments
Potassium	<3 mmol/L ≥5.5 mmol/L	FDA Feb 2005.
Glucose		
Hypoglycaemia	<2.2 mmol/L	CTCAE criteria.
Hyperglycaemia	>13.9 mmol/L (fasted)	CTCAE criteria.
Albumin	≤25 g/L	
Thyrotropin	< LLN > ULN	
Cholesterol	≥20% increase from baseline	D. M. Hegsted and Robert J. Nicolos, 1987 Demacker PN et al., 1982.
Triglycerides	≥20% absolute change from baseline	D. M. Hegsted and Robert J. Nicolos, 1987 Demacker PN et al., 1982.
Low-density lipoprotein-direct	≥20% increase from baseline	D. M. Hegsted and Robert J. Nicolos, 1987 Demacker PN et al., 1982.
High-density lipoprotein	≥ 20% decrease from baseline	D. M. Hegsted and Robert J. Nicolos, 1987 Demacker PN et al., 1982.
Hematology		
WBC	<3.0 Giga/L (Non-Black); <2.0 Giga/L (Black) ≥16.0 Giga/L	Increase in WBC: not relevant. To be interpreted only if no differential count available.
Lymphocytes	>4.0 Giga/L	
Neutrophils	<1.5 Giga/L (Non-Black); <1.0 Giga/L (Black)	International Consensus meeting on drug-induced blood cytopenias, 1991. FDA criteria.
Monocytes	>0.7 Giga/L	
Basophils	>0.1 Giga/L	
Eosinophils	>0.5 Giga/L or >ULN (if ULN≥0.5 Giga/L)	Harrison- Principles of internal Medicine 17th Ed., 2008.
Hemoglobin	≤115 g/L (Male); ≤95 g/L (Female) ≥185 g/L (Male); ≥165 g/L (Female) Decrease from Baseline ≥20 g/L	Criteria based upon decrease from baseline are more relevant than based on absolute value. Other categories for decrease from baseline can be used (≥30 g/L, ≥40 g/L, ≥50 g/L).
RBC	≥6 Tera/L	
Platelets	<100 Giga/L ≥700 Giga/L	International Consensus meeting on drug-induced blood cytopenias, 1991.

Table 12-4 Threshold Value Criteria for ECGs

Parameter	Comments
HR	≤ 50 bpm and decrease from baseline ≥ 10 bpm ≥ 120 bpm and increase from baseline ≥ 10 bpm
PR	≥ 220 ms and increase from baseline ≥ 20 ms
QRS	≥ 120 ms
QTc	Absolute values (ms)
Borderline	Borderline: 431-450 ms (Male); 451-470 ms
Prolonged*	(Female)
Additional	Prolonged: >450 ms (Male); >470 ms (Female) ≥ 500 ms
	Increase from baseline
	Borderline: Increase from baseline 30-60 ms
	Prolonged: Increase from baseline >60 ms

Note: Based on CPMP 1997 guideline.

Table 12-5 Threshold Value Criteria for Vital Signs

Parameter	PCS	Comments
HR	≤ 50 bpm and decrease from baseline ≥ 20 bpm ≥ 120 bpm and increase from baseline ≥ 20 bpm	To be applied for all positions (including missing) except STANDING.
SBP	≤ 90 mmHg and decrease from baseline ≥ 20 mmHg ≥ 160 mmHg and increase from baseline ≥ 20 mmHg	To be applied for all positions (including missing) except STANDING.
DBP	≤ 45 mmHg and decrease from baseline ≥ 10 mmHg ≥ 110 mmHg and increase from baseline ≥ 10 mmHg	To be applied for all positions (including missing) except STANDING.
Weight	$\geq 5\%$ increase from baseline $\geq 5\%$ decrease from baseline	FDA criteria Feb 2007.

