9 STATISTICAL ANALYSIS

9.1 General Considerations

The Schedule of Assessments is provided in Section 3 of CSP. The precision standards for reporting safety and efficacy variables are provided in an internal Biometrics document that specifies the programming rules including the precision for derived variables.

All individual subject data, including those derived, for subjects who were randomized or received at least 1 dose of study drug, i.e. All Subjects Set, will be presented in individual subject data listings as described.

Continuous variables will be summarized using the following descriptive summary statistics: the number of subjects (n), mean, standard deviation (SD), standard error (SE), median, minimum value (min), and maximum value (max).

Categorical variables will be summarized using counts and percentages.

Baseline value for the NRS via daily diary and the DSIS will be defined as the average score of at least 4 nonmissing scores from Day -7 to Day -1. For all other variables baseline will be defined as the most recent nonmissing measurement collected before the initial administration of study drug unless specified otherwise.

Change (absolute change) from baseline will be calculated as post-baseline value – baseline value unless otherwise specified.

Treatment-emergent (TE) Period will be defined as the time from dosing with study drug until the following time point:

- For enrolled subjects who have a Safety Follow-up Visit: through the Safety Follow-up Visit
- For enrolled subjects who do not have a Safety Follow-up Visit, the earliest of
 - 35 days after the last dose of study drug, or
 - the ETT Visit if that visit is 3 weeks or later following the last dose of study drug (see Section 9.1.5 of CSP)

Unscheduled visits: Unscheduled visit measurements will be included in analysis as follows:

- In scheduled visit windows per specified visit windowing rules.
- In the derivation of baseline/last on-treatment measurements.
- In the derivation of maximum/minimum on-treatment values and maximum/minimum change from baseline values for safety analyses.
- In individual subject data listings as appropriate.

Visit windowing rules: The analysis visit windows for protocol-defined visits are provided in [Appendix A](#).

Incomplete/missing data will not be imputed, unless otherwise specified.

Outliers: No formal statistical analyses will be performed to detect or remedy the presence of statistical outliers, unless specified otherwise.

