9.4.2 Clinical Laboratory Assessments

All statistical analyses of laboratory values will be performed using International System of Units. The raw values and change from baseline values for the continuous hematology, clinical chemistry will be summarized by treatment group at each scheduled visit. The threshold value criteria for hematology and clinical chemistry laboratory tests are provided in [Appendix D](#). The number and percentage of subjects with at least 1 hematology and clinical chemistry laboratory measurement meeting the threshold value criteria will be summarized

by treatment group at each scheduled visit. Coagulation results will be summarized by treatment group at each scheduled visit. The number and percentage of subjects with abnormal coagulation values at each scheduled time point will be summarized.

A listing containing individual subject hematology and clinical chemistry laboratory measurements meeting the threshold value criteria at any visit will be provided. For each subject in the listing, laboratory measurements at all visits will be included. This listing will include data from scheduled and unscheduled time points. Abnormal coagulation and urinalysis results also will be listed separately. For each subject in the listing, coagulation and urinalysis results at all visits will be included. Results of the urine/serum pregnancy test will be presented in individual subject data listings only.

Clinically significant abnormal laboratory findings will be reported as AEs.

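### The triglyceride threshold in SAP Table 12-3 names no adverse direction; read as a magnitude, it counts falls with rises and dilutes the by-arm comparison.

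*SAP*

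**What the plan says.** Table 12-3 in SAP Appendix D sets four lipid criteria at 20%, all citing the same two sources:

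- Cholesterol and directly measured LDL: "≥20% increase from baseline".
- HDL: "≥ 20% decrease from baseline".
- Triglycerides: "≥20% absolute change from baseline".

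SAP 9.4.2 says how the criteria are used: "The number and percentage of subjects with at least 1 hematology and clinical chemistry laboratory measurement meeting the threshold value criteria will be summarized". These counts are split by arm and visit. The same criteria decide which subjects enter the threshold listing.

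Two other outputs in SAP 9.4.2 bear on the point. One is the continuous summary: "The raw values and change from baseline values for the continuous hematology, clinical chemistry will be summarized by treatment group at each scheduled visit". The other is the content of the listing: "For each subject in the listing, laboratory measurements at all visits will be included".

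SAP 9.1 contains the only definition of the term used in the triglyceride row: "Change (absolute change) from baseline will be calculated as post-baseline value – baseline value unless otherwise specified".

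**The concern.** A threshold table exists to show how many subjects on each arm moved in a worrying direction. Three lipid rows do that. The triglyceride row gives no direction, and its natural reading is the size of the change whatever the sign. Where this SAP wants both directions, it writes two criteria: weight in Table 12-5 has separate lines for increase and decrease, and sodium, potassium and chloride have separate low and high limits. One undirected percentage departs from that practice.

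The definition in SAP 9.1 does not settle the matter. It describes a signed difference in the units of measurement, and a 20% limit does not apply directly to such a difference. One programmer could code the magnitude of the percentage change and another the signed percentage change, and the two tables would differ.

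Under the magnitude reading, a drug that raises triglycerides moves subjects above +20% and also moves subjects out of the group below -20%. Only the net of the two reaches the by-arm percentage. Subjects whose only crossing was a fall would also appear in the threshold listing.

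**Working it through.** The documents give no figure for triglycerides (no SD, event rate or power), so there is nothing of the plan's own to reproduce. What follows illustrates the size of the effect under stated assumptions.

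**Inputs**

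- From the documents: limits of +20% and -20% (Table 12-3 read as a magnitude); 114 / 2 = 57 subjects per arm (SAP 7.2 and 7.3).
- Assumed: log-normal values; within-subject CV 15 to 30%; no shift on placebo; a true 20% rise on VX-150 (ratio r = 1.2).
- Assumed as a yardstick only: a two-sided 5% comparison of proportions. The SAP plans no test on this table.

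**Formulas**, for one visit

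- SD of the log ratio of post-baseline to baseline: s = √2 × √ln(1 + CV²)
- Rise: P(ratio ≥ 1.2) = 1 − Φ((ln 1.2 − ln r) / s)
- Fall: P(ratio ≤ 0.8) = Φ((ln 0.8 − ln r) / s)
- Power = Φ((Δ − 1.96 × SE₀) / SE₁), with SE₀ pooled and SE₁ unpooled

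**Worked case, CV 20%**

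- s = 1.414 × √ln(1.04) = 0.280; ln 1.2 = 0.182; ln 0.8 = −0.223.
- Placebo: rise 1 − Φ(0.651) = 25.8%; fall Φ(−0.797) = 21.3%; together 47.0%.
- VX-150: rise 1 − Φ(0) = 50.0%; fall Φ(−1.448) = 7.4%; together 57.4%.
- Rise-only difference: 50.0 − 25.8 = 24.2 points. Rises plus falls: 57.4 − 47.0 = 10.4 points.

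**Across the assumed range** (true 20% rise, computed before rounding)

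| CV | Placebo: rise + fall | VX-150: rise + fall | Difference, rise only | Difference, both | Share kept | Yardstick power, rise only / both |
|---|---|---|---|---|---|---|
| 15% | 19.4 + 14.5 = 33.9% | 50.0 + 2.7 = 52.7% | 30.6 | 18.9 | 62% | 94% / 53% |
| 20% | 25.8 + 21.3 = 47.0% | 50.0 + 7.4 = 57.4% | 24.2 | 10.4 | 43% | 77% / 20% |
| 25% | 30.0 + 26.1 = 56.1% | 50.0 + 12.2 = 62.2% | 20.0 | 6.1 | 31% | 59% / 10% |
| 30% | 33.0 + 29.5 = 62.6% | 50.0 + 16.4 = 66.4% | 17.0 | 3.9 | 23% | 45% / 6% |

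The differences in points do not depend on the number of subjects; only the power does. With no drug effect, 34 to 63% of subjects would be flagged at a visit, and 15 to 30 points of that would be falls.

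**Larger effect.** For a true 50% rise, the combined rule gives differences of 52, 33, 21 and 14 points at CV 15, 20, 25 and 30%, with yardstick power of 100, 96, 68 and 39%.

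**The other planned summary.** As a proxy for the change-from-baseline table, compare mean log ratios for the 20% rise. At CV 20% this gives Φ(0.182 / (0.280 × √(2/57)) − 1.96) = Φ(1.51), about 93%. Across CV 15 to 30% the figure runs from over 99% down to 65%.

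**The case against.** The strongest answer is that SAP 9.1 makes absolute change a signed quantity. Expressed as a percentage of baseline, a limit of at least 20% would then catch rises only, which is the rule one would want. This shows that the two-directional reading is not certain. It does not rescue the wording. The definition is a difference in units, and if a signed rise were meant, the row would mean the same as its cholesterol and LDL neighbours while using a different word.

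A reader might go further and infer that falls cancel rises, that the table could hardly show a drug that raises triglycerides, or that the plan hides such harm. The documents do not support this.

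- Falls add to the count. The contrast shrinks because the arm with more rises has fewer falls, and the offset is partial: 23 to 62% of the rise-only difference remains in the illustration.
- A contrast close to zero arises only for modest rises with higher variability, and the variability is an assumption. A 50% rise stays visible at low to moderate CV.
- SAP 9.4.2 also plans a by-arm change-from-baseline summary at each visit, and the listing gives every visit for each flagged subject. Both show direction.
- No test is planned on the threshold table, so the power figures describe no planned inference. Nor does meeting the criterion make a value an adverse event: under SAP 9.4.2 only clinically significant abnormal findings are reported as AEs.

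These points stand, and they limit the concern to one descriptive table and its listing. They do not remove it: a mean change does not say how many subjects rose by at least 20%, which is the question a threshold count answers.

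The creatinine rows also omit a direction, but the case there is weak. A 100% fall would require a value of zero, so that criterion can only be a rise; only the 30% criterion could be misread.

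**Conclusion.** The point holds in limited form. The triglyceride criterion has no stated adverse direction, is inconsistent with the other lipid rows and with how the SAP handles two-sided criteria elsewhere, and on its natural reading pools falls with rises. For an assumed true 20% rise and within-subject CV of 15 to 30%, this cuts the by-arm difference from about 31 to 17 points down to about 19 to 4 points. The CV, the log-normal model and the size of the rise are assumptions. Post-screening samples need fasting only in relation to dosing (Protocol 11.6.2), which may place variability toward the upper end, but the documents do not quantify it. If the row were programmed as a signed percentage, there would be no dilution, and only the unclear wording would remain. Efficacy analyses and the other safety summaries are untouched.

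**What to change.** Before database lock, reword the triglyceride row of Table 12-3 to "≥20% increase from baseline", the form used for cholesterol and LDL. Alternatively, keep both directions but tabulate increases and decreases of at least 20% on separate lines, as Table 12-5 does for weight.

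Either change is a few words in an appendix plus a matching line in the programming specification. With the increase-only wording, falls are no longer flagged, but they stay in the change-from-baseline summary. The two-line version loses nothing and adds one table row.

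Optionally, state that the 30% creatinine criterion refers to an increase. This is a clarification of wording only.
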